1.9 STUDY ENDPOINTS

Primary endpoint:

• Stroke (fatal and nonfatal ischemic stroke) in the vertebrobasilar territory at 12 months.

Secondary endpoints:

- TIA and fatal and nonfatal ischemic stroke in the vertebrobasilar territory.
- Ischemic stroke in any vascular territory.
- All ischemic stroke and vascular death.
- The aggregate of ischemic stroke, myocardial infarction and vascular death.
- All stroke (ischemic and hemorrhagic).
- All death (vascular and nonvascular).
- Neurological impairment as determined by the NIH Stroke Scale.
- Neurological disability as determined by the modified Barthel Index.
- Handicap as determined by the modified Rankin Scale and Glasgow Outcome Score.

Ischemic stroke is defined as new neurological symptoms or signs lasting at least 24 hours or lasting less than 24 hours but associated with new infarct on CT or MRI. TIA is defined as new neurological symptoms or signs lasting less than 24 hours without radiographic correlate of infarct. Vascular death is defined as a death of known vascular etiology or sudden death that could not be explained by a known nonvascular process.

Initial determination of endpoints will be defined by the participating site study physician but will be ultimately be independently determined by a central adjudication committee.

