Patients will be placed on a standard medical regimen to include antithrombotic agents and standard stroke/cardiovascular risk factor medical therapy as managed by the participating center study physician in conjunction with the patient's primary care physician.

Follow-up evaluations

Monthly telephone follow-up assessment

The participating site study coordinator will contact patients monthly by telephone until 12 months for determination of new events. If a potential endpoint is identified treating physician will be notified, and the participating site arranges for the patient to be evaluated by the blinded study physician within 72 hours. If a stroke is clinically suspected, brain imaging with CT or MR will be performed in accordance with standard clinical management. The data from the telephone interviews will be recorded using standardized web-based case report forms.

Clinical visit follow-up assessment

In person follow-up will be performed at the participating site at 6 months (m), and 12m as a minimum, and every 6m thereafter up until completion of the study or 2 years maximum. A detailed neurological evaluation and assessment for new symptoms or signs will be performed at these visits. Interval occurrence of any symptoms of cerebrovascular disease or other medical problems will be determined. Clinical evaluations will be performed by the blinded study physician unfamiliar with the results of the study MR imaging. The patient's medication regimen and NIHSS Score will be recorded. The data will be recorded using standardized web based data forms.

MR imaging follow-up assessment

The MR imaging protocol will be repeated at 6m and 12m, at a minimum, and at 24 months if prior to the completion of the study. Results will be centrally reviewed and the results will remain blinded from the participating center.

Time course of assessments and follow-ups

| MONTHS | 0 | 1* | 2* | 3* | 4* | 5* | 6* | 7* | 8* | 9* | 10* | 11* | 12* | 18 | 24 |
|---------------------|---|----|----|----|----|----|----|----|----|----|-----|-----|-----|----|----|
| Demographics | х | | | | | | | | | | | | | | |
| Baseline Evaluation | х | | | | | | | | | | | | | | |
| Angiogram/CTA | х | | | | | | | | | | | | | | |
| MR imaging | х | | | | | | х | | | | | | Х | | Х |
| Telephone interview | | х | х | Х | х | х | х | х | х | х | Х | Х | Х | | |
| Clinical Follow-up | х | | | | | | х | | | | | | Х | х | Х |
| Evaluation | | | | | | | | | | | | | | | |

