1.10 DATA ANALYSIS

A dedicated Biostatistician and Director of the Data Management Center for the Center for Stroke Research at the UIC Department of Neurology and Rehabilitation, UIC will oversee all statistical analysis of the study.

Analysis

Analysis of the primary endpoint (ischemic stroke in the vertebrobasilar territory) will consist of time-to-endpoint comparison using the log-rank test between patients designated as 'low flow' versus 'normal flow'. The designation of flow status will be based upon the patient's initial enrollment QMRA study, using parameters defined in the preliminary studies. Adjusted analysis will be performed using multivariate logistic and proportional hazard regression models to examine stroke incidence adjusted for key confounders. Post-hoc sensitivity analysis will be

performed to examine alternative cut-points for designation of low or normal flow status, and to examine the predictive value of each MR imaging modalities (QMRA and MR perfusion) and whether the combination of the two modalities provides a better indicator of stroke risk than either alone. Patients will be censored from analysis at the time of any crossovers to interventional procedures.

Sample size calculations

Sample size estimates are based upon stroke rates from published preliminary data²³, which indicate a 71% and 100% one year stroke free survival in the 'low flow' and 'normal flow' groups, respectively, translating into annual event rates of 0.29 and 0.0. Although our data indicated a 0 stroke rate in the 'normal' flow group, there was a 0.04 rate of TIA, which can occur on a clinical spectrum with stroke. As a result the sample size calculations were based on a conservative estimate of 0.02 event rate in the normal flow group. Sample sizes were calculated for a range of possible event rates in the low flow group from 0.18 to 0.28. A 10% attrition rate was included in the calculations. Based upon these estimates, a total sample size of 80 patients will achieve approximately 80% power in detecting a significant difference between the groups with an annual event rate of 0.22 in the low flow group. Exploration for risk factors and adjustment for covariates will be performed with Cox proportional hazards analysis.

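### Does the ischemic-stroke definition let a hemorrhage or a stroke mimic count as a primary event?

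*Protocol*

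**What the plan says.** The primary endpoint in sections 1.1 and 1.9 is fatal or nonfatal ischemic stroke in the vertebrobasilar territory, taken at 12 months. Section 1.9 then gives a definition with two limbs:

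- 24-hour limb: "Ischemic stroke is defined as new neurological symptoms or signs lasting at least 24 hours".
- Short limb: "or lasting less than 24 hours but associated with new infarct on CT or MRI".

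The next sentence reads "TIA is defined as new neurological symptoms or signs lasting less than 24 hours without radiographic correlate of infarct". Vascular death, in the same paragraph, includes "sudden death that could not be explained by a known nonvascular process". A separate secondary endpoint counts ischemic and hemorrhagic stroke together. The site physician makes the first determination of each endpoint, and the final one is "independently determined by a central adjudication committee". The dated footnote in section 1.1 reports the same two-limb sentence as the committee's definition.

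Under the monthly telephone follow-up in section 1.8, a potential endpoint leads to evaluation by a blinded study physician within 72 hours. If stroke is suspected, "brain imaging with CT or MR will be performed in accordance with standard clinical management". The primary analysis in section 1.10 is a "time-to-endpoint comparison using the log-rank test" between low-flow and normal-flow patients.

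**The concern.** Parsed strictly, the infarct condition belongs only to events shorter than 24 hours, and the TIA sentence confirms that reading. For longer events the text asks only that symptoms be new and last a day. A cerebellar hemorrhage or a lasting brainstem mimic would meet those words. The footnote seems to weaken the usual answer that adjudication will sort it out, because the committee is said to work from this very sentence. Vascular death carries a condition on cause, which makes its absence from stroke and TIA stand out.

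The planned event count is small. Section 1.10 assumes an annual rate of 0.02 with normal flow, which is less than one expected event in that group. A single wrongly counted event there could matter to the log-rank comparison, so the definition deserves a check.

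**Working it through.** **1. Reading the text as a whole.** An event must pass three tests to be primary: it is an ischemic stroke, it belongs to the vertebrobasilar territory, and it falls within 12 months. The two-limb sentence sits directly before the TIA sentence, and the two share one structure of duration and infarct. Together they draw the line between stroke and TIA. The line between ischemic and hemorrhagic stroke is drawn by the endpoint names, since hemorrhage enters only through the all-stroke endpoint. To count a hemorrhage as primary, the committee would have to disregard the word being defined.

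**2. Safeguards against hemorrhage and mimics.**

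| Safeguard | Section |
|---|---|
| Neurological disease that would confound follow-up is excluded at entry | 1.6 |
| Potential events found by telephone are seen by a blinded physician within 72 hours | 1.8 |
| CT or MR when stroke is suspected | 1.8 |
| Event must be attributed to the vertebrobasilar territory (primary endpoint) | 1.1, 1.9 |
| Central committee makes the final determination | 1.9 |

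**3. The plan's own power figure.** Inputs from section 1.10: rates 0.22 and 0.02, N = 80, 10% attrition. Two-sided 0.05 and an equal split are assumptions, since the protocol states neither. For two proportions with pooled variance, the power is Φ(z), where

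z = [0.20·√n − 1.96·√(2·0.12·0.88)] / √(0.22·0.78 + 0.02·0.98).

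With n = 40: z = (1.265 − 0.901)/0.437 = 0.83, so power is 79.8%. This matches the stated figure of about 80%.

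**4. Expected events.** After attrition 80 × 0.9 = 72 patients remain, or 36 per group. Low flow: 36 × 0.22 = 7.9. Normal flow: 36 × 0.02 = 0.7. With 40 per group the figures are 8.8 and 0.8.

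**5. One added normal-flow event, log-rank test, 36 per group** (p over random event orders, no censoring before the last event):

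| Low vs normal events | Median p | Range |
|---|---|---|
| 8 vs 1 | 0.013 | 0.012–0.015 |
| 8 vs 2 | 0.042 | 0.035–0.051 |
| 7 vs 1 | 0.026 | 0.023–0.028 |
| 7 vs 2 | 0.077 | 0.066–0.089 |

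The pattern nearest the plan, 8 vs 1, stays below 0.05 in about 98% of orders after the extra event. The 7 vs 1 pattern does not.

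**6. Where the false event falls.** These figures come from 20,000 simulated trials with exponential times, 12 months of follow-up and 36 per group. Baseline log-rank power is about 83%.

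- Event forced into the normal-flow group: about 25% of significant trials are reversed.
- Event placed in a random patient: about 13% of significant trials are reversed, and about 20% of non-significant trials become significant.

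The second case is the relevant one, because flow results are withheld from the patient and from site personnel, including the evaluating physician (section 1.8). If every trial contained exactly one such event, power would change by about −0.83 × 0.13 + 0.17 × 0.20 = −0.11 + 0.03 = −0.08, to roughly 75%.

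**7. Assumed false-event rates, equal in both groups.** Adding 1, 2 or 3 percentage points lowers the simulated power from about 83% to 78%, 73% or 69%. In 72 patients these rates mean 0.7 to 2.2 false events against 7.92 + 0.72 = 8.64 true ones, or 8% to 25% extra events after imaging and adjudication. The protocol gives no such rate, and the upper values are hard to credit.

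**The case for a change.** The strongest case for a change is that this is text the protocol fixes for its primary endpoint, so it cannot be put down to detail left for a later document. The committee is reported to use the sentence, imaging results are not formally tied to the 24-hour limb, and patients receive antithrombotic agents, so hemorrhage is not far-fetched. The secondary endpoints on ischemic stroke in any territory lack even the territory condition. A few words on presumed ischemic origin would cost almost nothing.

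The grammatical point stands: the limb does not state a cause, and the low cost of extra wording is not in dispute. What does not stand is the step from there to miscounted events. The footnote shows the committee's definition but not its procedures, and the question put to the committee is still whether an ischemic stroke occurred. Requiring hemorrhage and mimics to be excluded on CT or MRI would do harm: fatal stroke is part of the endpoint, and a patient who died before imaging could then never qualify.

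**Conclusion.** The 24-hour limb relies on the endpoint's name for its ischemic condition. That is a gap in wording which adjudicators fill sensibly, and the rest of the protocol shows how they should fill it. Spelling out a presumed ischemic cause would record existing intent without altering which events a competent committee counts, so no expected result changes and no amendment is needed.

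If some false events did get through, they should arise regardless of flow and weaken the contrast; they should not create one. A single such event would reverse about 13% of significant results and push about 20% of non-significant ones the other way. These figures assume 36 patients per group, two-sided 0.05 and the planned rates of 0.22 and 0.02. The split matters to the baseline: with 48 low-flow and 24 normal-flow patients, power starts at about 67% and falls to 63%, 58% or 55% under the assumed 1, 2 or 3 points. All of this is illustration, because the protocol supplies no false-event rate and shows no miscounted event.

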1.10 DATA ANALYSIS

A dedicated Biostatistician and Director of the Data Management Center for the Center for Stroke Research at the UIC Department of Neurology and Rehabilitation, UIC will oversee all statistical analysis of the study.

Analysis

Analysis of the primary endpoint (ischemic stroke in the vertebrobasilar territory) will consist of time-to-endpoint comparison using the log-rank test between patients designated as 'low flow' versus 'normal flow'. The designation of flow status will be based upon the patient's initial enrollment QMRA study, using parameters defined in the preliminary studies. Adjusted analysis will be performed using multivariate logistic and proportional hazard regression models to examine stroke incidence adjusted for key confounders. Post-hoc sensitivity analysis will be

performed to examine alternative cut-points for designation of low or normal flow status, and to examine the predictive value of each MR imaging modalities (QMRA and MR perfusion) and whether the combination of the two modalities provides a better indicator of stroke risk than either alone. Patients will be censored from analysis at the time of any crossovers to interventional procedures.

Sample size calculations

Sample size estimates are based upon stroke rates from published preliminary data²³, which indicate a 71% and 100% one year stroke free survival in the 'low flow' and 'normal flow' groups, respectively, translating into annual event rates of 0.29 and 0.0. Although our data indicated a 0 stroke rate in the 'normal' flow group, there was a 0.04 rate of TIA, which can occur on a clinical spectrum with stroke. As a result the sample size calculations were based on a conservative estimate of 0.02 event rate in the normal flow group. Sample sizes were calculated for a range of possible event rates in the low flow group from 0.18 to 0.28. A 10% attrition rate was included in the calculations. Based upon these estimates, a total sample size of 80 patients will achieve approximately 80% power in detecting a significant difference between the groups with an annual event rate of 0.22 in the low flow group. Exploration for risk factors and adjustment for covariates will be performed with Cox proportional hazards analysis.

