1.2 OBJECTIVES

Primary Objective:

• To test the hypothesis that among patients with symptomatic vertebrobasilar disease (VBD), those with distal blood flow compromise are at higher risk of subsequent posterior circulation stroke than those with normal flow.

Secondary Objectives:

- To determine the correlation between large vessel flow (QMRA) and tissue level perfusion (MR perfusion) in the posterior circulation, and the predictive value of each modality.
- To determine other predictive factors for stroke in this population.
- To determine the hemodynamic effects of varying degrees of vertebrobasilar stenosis and occlusion.
- To determine changes in hemodynamic status of patients on medical therapy over time.
- To determine the utility of QMRA as a non-invasive screening and monitoring tool in symptomatic vertebrobasilar disease (VBD).

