1.3 BACKGROUND AND RATIONALE

Approximately 700,000 strokes occur annually in the U.S. making it the third leading cause of death and the leading cause of permanent disability among adults. Posterior circulation strokes account for 30-40% of all ischemic strokes, resulting in approximately 200,000 cases per year. Atherosclerotic disease of the vertebrobasilar system is an important etiology of posterior circulation stroke¹. **Symptomatic vertebrobasilar disease (VBD)** carries a high annual risk of stroke, averaging 10-15% per year despite medical therapy. Vertebrobasilar stroke is particularly prone to resulting in devastating consequences due to the concentrated 'eloquence' of brain tissue supplied by the posterior circulation ². Consequently, vertebrobasilar stroke can result in high rates of death and disability.

Risks of stroke in VBD

Several retrospective studies have estimated the risk associated with vertebrobasilar stenosis (50-99%) to be **10-15% per year** ³⁻⁵. These stroke rates approach those seen with symptomatic high grade extracranial carotid stenosis. In a retrospective study of 44 patients with distal vertebral artery (VA) or basilar artery (BA) stenosis of \geq 50%, Mouffarij et al. reported a 27% incidence of vertebrobasilar ischemic events, with 5 of 12 events being stroke rather than TIA³. An overall 80% stroke free survival at 2 years was evident in this study. A study by Qureshi et al. of 102 patients with symptomatic VBD (>50% stenosis) demonstrated that 14% of patients experienced recurrent stroke, with a stroke free survival of only 72% at two years⁵. Retrospective analysis from the WASID study group⁶ examined the risk of stroke in 68 patients with symptomatic intracranial vertebrobasilar 50-99% stenosis treated with aspirin or warfarin over a median follow-up of 13.8 months. Fifteen (22%) of the patients suffered stroke, of which four (27%) were fatal. They reported an overall stroke risk of 13.6 to 15 per 100 patient years for stroke in the territory of the stenotic artery⁴. Data from the prospective WASID trial comparing use of warfarin versus aspirin in symptomatic intracranial stenosis of 50-99% in 569 patients demonstrated that 15% of patients suffered stroke in the territory of the stenotic artery⁷. The

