incidence of stroke at one year was 12%, with stroke rates that were not significantly different between the anterior and posterior circulation⁸. In another recent prospective study of patients with intracranial stenosis \geq 50%, ischemic events were reported for the 49 patients of the full cohort of 102 patients who harbored symptomatic vertebral or basilar disease. The frequency of recurrent ischemic events (TIA and stroke combined) was found to be 42.8% during a mean follow-up of 23.4 months⁹.

The predominant stroke mechanism for patients with VBD appears to be regional hypoperfusion¹⁰; although thrombotically active plaques are a prominent feature of symptomatic carotid disease, this mechanism appears less prominent as the primary cause of ischemia related to vertebrobasilar stenosis. The posterior circulation vascular anatomy can allow for potential compensations to maintain distal arterial territory flow through collaterals (such as the posterior communicating arteries) in the setting of proximal vessel stenosis or occlusion. The existence and extent of these compensatory blood flow pathways, therefore, may influence the risk of stroke.

Rationale for use of QMRA and MR Perfusion

Various imaging techniques exist for assessing cerebrovascular hemodynamic compromise, including SPECT, PET, Xenon CT and TCD. These modalities are generally aimed at assessing cerebral tissue perfusion, and have proven valuable in assessment of anterior circulation flow compromise. However, these modalities have been less useful in the posterior circulation due to factors such as inadequate spatial resolution for the compact brain territory involved, and bony skull base artifacts. An alternative strategy is therefore desirable. Measurement of large vessel flow in affected and major collateral vessels in the posterior circulation is one such strategy, and can be obtained non-invasively using phase contrast QMRA¹¹⁻¹⁴. QMRA imaging can be easily combined with MR perfusion imaging to provide both large vessel and tissue level hemodynamic assessment.

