The technique of phase contrast QMRA allows volumetric flow to be measured directly and noninvasively in the craniocervical vasculature, and has been shown to be accurate in both the in vitro and in vivo setting¹⁵⁻¹⁹. Standardized QMRA software is available as NOVA (Noninvasive Optimal Vessel Analysis), and has been used extensively to assess patients with cerebrovascular disease at the central coordinating site, University of Illinois at Chicago (UIC). A retrospective non-blinded cohort study examining outcomes of patients with symptomatic VBD demonstrated a significantly higher risk of subsequent stroke in patients with hemodynamic impairment as assessed by NOVA QMRA. Furthermore, QMRA may provide an appropriate non-invasive screening and follow-up monitoring tool in patients with known or suspected VBD.

Unlike QMRA which provides information regarding volumetric flow within a given vessel, MR perfusion imaging provides characterization of tissue level perfusion in the brain territory of interest²⁰. MR perfusion imaging is readily available on most clinical scanners, and can provide information regarding tissue level hemodynamic compromise. Therefore, tissue perfusion measurements may provide important correlative and predictive data for the conductance flow data from the large vessels obtained using phase contrast QMRA.

Rationale for the VERiTAS study

VBD represents a potentially treatable high risk source of stroke. Advances in endovascular angioplasty and stenting have created new options for the treatment of VBD, but the interventions themselves carry significant risks^{21, 22}, and the selection criteria for appropriate candidates remains uncertain. Our preliminary published retrospective data²³ suggests that the

risk of stroke in VBD is affected by the extent to which intracranial blood flow is compromised. Specifically, our analysis has indicated that patients with low intracranial flow as assessed by noninvasive QMRA are at significantly higher risk of stroke than those with normal flow. The objective is now to conduct a prospective longitudinal study of patients with symptomatic VBD to determine if level of blood flow compromise assessed by QMRA and MR perfusion at the baseline examination predicts risk of recurrent ischemic events.

[figure not shown]

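### The flow-status regression models may have no finite ratio, because the normal-flow group may have no stroke; a penalised fit should be named, and the MR perfusion analysis should not be called post-hoc

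*Protocol*

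**What the plan says.** Section 1.10 (Analysis) makes the log-rank comparison of low with normal flow, by baseline QMRA, the primary analysis. It then plans an adjusted analysis of stroke incidence with "multivariate logistic and proportional hazard regression models".

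Section 1.10 (Sample size calculations) takes 80 patients, 10% attrition, and annual event rates of 0.22 for low flow and 0.02 for normal flow. It reports that the preliminary data had no stroke at all in the normal-flow group.

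On imaging, section 1.10 continues: "Post-hoc sensitivity analysis will be" done for two purposes. One is alternative cut-points. The other is "to examine the predictive value of each MR imaging modalities (QMRA and MR perfusion", and whether the two combined do better than either alone. Section 1.2 lists as a secondary objective the correlation between the modalities "and the predictive value of each modality". Section 1.9 lists as a secondary endpoint "TIA and fatal and nonfatal ischemic stroke in the vertebrobasilar territory".

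**The concern.** A regression ratio for flow status can be estimated only if both flow groups have at least one event. Section 1.10 plans for a rate at which the normal-flow group may well have none, and the preliminary study it relies on had none. The maximum-likelihood ratio is then infinite. Software either fails to converge or prints a huge ratio with a huge standard error. Adding covariates does not help, since a flow category without events stays without events. The adjusted result, which is meant to show that the flow effect is not explained by confounders, would be unusable even though the data point strongly in the expected direction.

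The second matter is a label. An analysis written in advance to serve a listed objective is not post-hoc, and what perfusion predicts is not a sensitivity check of a QMRA comparison. A reader of section 1.10 alone could not tell that the perfusion result answers an objective while the cut-point search is exploratory.

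**Working it through.** **Inputs.** From section 1.10: 80 patients, 10% attrition, rates 0.22 and 0.02. The protocol gives no low-flow share *s*, so I assume 25%, 50% and 70%. It states no probability of an empty group, so there is no figure of its own to reproduce.

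**Patients.** 80 × 0.90 = 72. Normal-flow patients = 72(1 − s).

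**Chance of no normal-flow stroke.** 0.98^(72(1 − s)) over 12 months, with twice the exponent over 24 months.

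| s | Normal-flow patients | Expected strokes, both groups, 12 months: 72(0.22s + 0.02(1 − s)) | No normal-flow stroke, 12 months | Same, all followed 24 months |
|---|---|---|---|---|
| 25% | 54 | 5.0 | 0.98^54 = 34% | 0.98^108 = 11% |
| 50% | 36 | 8.6 | 0.98^36 = 48% | 0.98^72 = 23% |
| 70% | 21.6 | 11.5 | 0.98^21.6 = 65% | 0.98^43.2 = 42% |

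With no attrition at all, the 50% case is 0.98^40 = 45%, so the result does not hang on the attrition figure.

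**What the ordinary fit does.** Take s = 50% and the rounded expected count: 0.22 × 36 ≈ 8 low-flow strokes among 36, none among 36 with normal flow, no censoring before the last stroke.

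- Odds ratio: odds of 8/28 in low flow against odds of 0/36 in normal flow, infinite.
- Hazard ratio h: before the i-th stroke (i = 1 to 8), n = 37 − i low-flow and 36 normal-flow patients are at risk. Each stroke contributes h/(nh + 36) to the partial likelihood. This rises with every increase in h, so there is no maximum.
- Wald test: each stroke adds p(1 − p) to the information, with p = nh/(nh + 36). Where an algorithm stops is arbitrary. At log h = 5, 10 and 15 the standard errors are 4.1, 49.7 and 606, so z = 1.2, 0.20 and 0.02. The test moves towards no effect as the estimate moves away from it.
- Log-rank test, same data: expected low-flow strokes Σ n/(n + 36) = 3.79, variance Σ [n/(n + 36)][36/(n + 36)] = 1.99, chi-square (8 − 3.79)²/1.99 = 8.9, p = 0.003. The primary test keeps working.

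**What a Firth fit does.** For the unadjusted logistic model it amounts to adding 0.5 to each cell: odds of 8.5/28.5 in low flow against odds of 0.5/36.5 in normal flow, a ratio of 21.8. The 95% profile interval, where twice the drop in penalised log-likelihood reaches 3.84, runs from 2.5 to about 2,860. For the Cox model, adding half the log of the information above to the log partial likelihood gives a hazard ratio of 18.9, interval 2.4 to about 2,450. The lower limit is usable. The upper limit shows honestly that the data barely bound the effect from above.

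**Behaviour over repeated samples.** The true hazard ratio at the protocol's rates is ln(0.78)/ln(0.98) = 12.3. In simulation at these rates the ordinary Wald test was never significant when the normal-flow group had no stroke, while the Firth estimate stayed finite with a median of about 8 to 11. That is the shrinkage. A single extreme estimate can still occur.

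**The label.** Section 1.2 covers the predictive value of each modality. For QMRA, section 1.10 already answers it with the primary log-rank test. For MR perfusion, the post-hoc sentence is the only analysis in section 1.10 that names it. The combination appears only in section 1.10 and is not a listed objective.

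**The case against.** The strongest reply is that the choice of fit is commonly left to a statistical analysis plan, which may exist here. That stands as far as severity goes: this is a cheap improvement, not an error that invalidates the study. But section 1.10 does name the two models, alongside a rate at which they often fail. One may also say that a likelihood-ratio test and a one-sided bound can be had without penalisation. True, but they give no point estimate.

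On the label, a reader of sections 1.2 and 1.10 together can work out what was meant, and relabelling alone changes no number. That also stands.

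Several stronger readings are tempting, and the protocol does not support them:

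- *The post-hoc label undermines both modalities.* It does not. QMRA prediction is the prespecified primary analysis, and listing it again as secondary would give one comparison two statuses.
- *The endpoint for prediction is contradictory.* Section 1.3 says baseline flow "assessed by QMRA and MR perfusion at the baseline examination predicts risk of recurrent ischemic events", and uses a similar term for TIA and stroke combined, but only in describing a cited cohort: "The frequency of recurrent ischemic events (TIA and stroke combined) was found to be 42.8% during a mean follow-up of 23.4 months". That does not define the term for this study. The mention of stroke risk in section 1.10 belongs to the clause on combining modalities.
- *TIA plus stroke would about double the events.* This rests on outside cohorts, such as the one "with 5 of 12 events being stroke rather than TIA", and not on the protocol's planning rates.
- *The perfusion analysis is underpowered.* Section 1.10 claims no power for it. Any calculation with 72 patients would also ignore those enrolled without gadolinium, who have no perfusion scan (section 1.6).

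**Conclusion.** The concern holds for the regression models. At the protocol's own rates there is roughly an even chance (48%; 34% to 65% over the assumed shares) that the ordinary 12-month ratio for flow status does not exist, and about 23% with full 24-month follow-up at a 50% share. This assumes independent patients, a constant 0.02 annual rate and 72 patients followed throughout. Censoring at crossover to intervention would shorten time at risk and raise these figures. A true normal-flow rate above 0.02 would lower them.

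The label conflict is real but minor, and is confined to MR perfusion. A reader might infer that the main comparison or the sample size is compromised. Neither is: the log-rank test works with no event in one group, and nothing here bears on the 80 patients.

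**What to change.** In section 1.10:

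1. State that any logistic or Cox model containing QMRA flow status uses a Firth-penalised fit with profile-likelihood intervals. The primary log-rank test stays as it is.
2. Take MR perfusion out of the post-hoc sentence. Make its predictive value a planned secondary analysis, reported as a hazard ratio with 95% interval on vertebrobasilar stroke and on the listed vertebrobasilar TIA-plus-stroke endpoint, among patients who had a perfusion scan. The choice of perfusion measure can be left to the SAP.
3. Keep alternative cut-points and the combination of modalities, labelled exploratory.

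The cost is a few sentences and one further run on an endpoint already collected, with no new data. The penalised ratio is pulled somewhat towards 1, which the report should say. TIA is a softer outcome than stroke, which is why both endpoints should be shown.
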